The total duration of this randomized, double-blind, placebo-controlled trial will be 2 years. For each participant the total duration of the study will be 14 weeks, including 8 weeks of intervention with SXB or PBO, preceded by a 4-week period of collection of baseline data, and followed by a 2-week period of data collection post-intervention. Subjects taking MLT or any other medication capable of affecting RBD other than clonazepam (CLZ) will maintain their regimen at fixed dose throughout the 14-week duration of the study. Those taking CLZ will proceed to reduction and discontinuation of CLZ, followed by a 2-week washout period prior to receiving study drug. If unable to discontinue CLZ prior to study drug, they will reduce CLZ to lowest acceptable dose by the end of the 4-week baseline period followed by cross-taper with SXB during the first 2 weeks of flexible dosing.

In each arm, dosage of SXB and PBO will be titrated up weekly (this weekly titration will occur via phone calls by the PI on days 2-6 after each new dose change) by up to 1.5g nightly dose increments from an initial 4.5g total nightly dose (which could be given

in two unequal doses if needed, or one single dose no greater than 4.5g) to an optimal individual dose based on clinical response on RBD symptoms and tolerability, to a maximum nightly dose of 9g ("flexible dose" period lasting up to 8 weeks). The optimal dose for each participant will then be continued for at least 4 weeks ("stable dose").

Flowchart

MOCA: Montreal Cognitive Assessment

PSG: Polysomnography

CGI: Clinical Global Impression questionnaires

- **Day 1 (Visit #1 = Initial visit with research coordinator):**
 - Verification of inclusion and exclusion criteria
 - Enrollment (if not performed prior)
 - Physical Exam (MoCA,
 - PSQI, PHQ-9, GAD-7, SCOPA-AUT, Epworth sleepiness scale
 - provide RBD logs and sleep diary for the 14 following weeks, 2 blank Karolinska scales, and two actigraphy devices (Philips Actiwatch2) to be worn on dominant wrist and ankle for one month

- instructions on when to complete Karolinska scale #1 (Day 21-27, one hour after waking up the day prior to sleep study) from home
 - Instructions on clonazepam taper, when applies
 - pregnancy testing for female subjects of childbearing age, when applicable
 - collection of adverse events (AEs)
 - MD (PI, coPI) will be available as needed via telephone or remote video conference system

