- **Day 1-28 (phone calls, weekly, when applicable):** guidance on downtitration of CLZ
- **Day 28 ± 7 days:** 1st video-PSG wearing home actigraphy device (Philips Actiwatch2) and additional wrist and ankle high-frequency actigraphy device (Xiaomi Amazfit Arc)
- **Day 29 (One day after Day 28 ± 7 days, Visit #2 = Randomization visit with research coordinator):**
 - Collection of 1-month RBD log and sleep diary
 - Collection of Karolinska scale #1
 - Collection of all actigraphy devices
 - Epworth sleepiness scale
 - Randomization
 - Subjects receive SXB or PBO and instructions on titration schedule
 - pregnancy testing for female subjects of childbearing age, when applicable
 - collection of adverse events (AEs)
 - MD (PI, coPI) will be available as needed via telephone or remote video conference system

Day 30-84 ± 7 days (phone calls): Every week after each new dose the subject will be called (including when the dose will remain stable), these phone calls will be made between day 2-6 to discuss response, record adverse events, and determine the next weeks titration dose.

- **Day 57-85 ± 7 days (Visit #3 = Interim visit with research coordinator):**
 - Collection of 1-month RBD log and sleep diary
 - Epworth sleepiness scale
 - PSQI, PHQ-9, GAD-7
 - Completion of CGI-E by participants
 - Completion of CGI-I by clinician
 - Physical Exam (including MoCA, orthostatic vital signs)
 - instructions on when to complete Karolinska scale #2 (Day 78-84, one hour after waking up the day prior to sleep study) from home
 - Participants provided with two actigraphy devices (Philips Actiwatch2) to be worn on dominant wrist and ankle for one month
 - pregnancy testing for female subjects of childbearing age, when applicable

- Collection of AEs, side effects
- MD (PI, coPI) will be available as needed via telephone or remote video conference system

- **Day 84-112 ± 7 days: 2nd video-PSG wearing home actigraphy device (Philips Actiwatch2) and additional wrist and ankle high-frequency actigraphy device (Xiaomi Amazfit Arc)**

- **Day 85-113 (One day after Day 84-112 ± 7 days, Visit #4 = Final Visit with research coordinator):**
 - Collection of high-frequency actigraphy device (Xiaomi Amazfit Arc)
 - Collection of 1-month RBD log and sleep diary
 - Collection of AEs, side effects
 - Collection of Karolinska scale #2
 - Epworth sleepiness scale
 - PSQI, PHQ-9, GAD-7, SCOPA-AUT
 - Completion of CGI-E by participants
 - Completion of CGI-I by clinician

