Participants will be randomized in a double-blind manner to either SXB or PBO. The duration of the intervention in both conditions will be no longer than 12 weeks, including up to 8 weeks of flexible dosing and 4 weeks of stable dosing. Treatment will be initiated with 4.5g dose of SXB or PBO, given nightly in two doses 2.5-4h apart according to the standard protocol used in narcolepsy. PBO will be similar in appearance, smell and flavor to the subjects, so that the investigators and participants will be unable to distinguish it from SXB. The dose will be increased or decreased by 0.5 - 1.5g weekly increments until reaching the optimal dose based on clinical response and tolerance, not exceeding 9g nightly. Evidence has shown that patients with RBD treated with sodium oxybate respond to nightly doses ranging from 3-6 g. Among these subjects, some have benefited from a 5 gram nightly dose. This flexibility in dosage is determined on an individual basis, in which the final dose must be both effective and tolerated. Dosage flexibility is essential as this older population with prodromal or overt signs of neurodegeneration may not require or tolerate the higher dosages used in patients with narcolepsy. Although the “default” regimen will be two equally divided doses 2.5-4hours apart, if required, the drug will be given in two unequal doses, or in one single dose, with no single dose allowed to be greater than 4.5g. Once optimal dose reached, fixed dose will be continued for at least 4 weeks and discontinued over one night. During the two weeks following discontinuation, data will continue to be collected. Patients will be allowed to resume usual treatment, including CLZ.

In this study, the choice of flexible dosing for patients receiving SXB is based on a few factors. From the 4 case reports summarized above, effective doses of SXB in patients with refractory RBD ranged from 3g to 6g nightly, one patient requiring uptitration of his initial 5g dose to 6g. No adverse events or side effects were reported by the authors. In patients with narcolepsy, the efficacy of SXB is dose-dependent, showing superior efficacy with 9g nightly dose compared to 6g. Taken together, this data suggests that higher SXB doses will be more likely to control RBD symptoms, however with a higher risk of side effects. In the two studies evaluating SXB efficacy and tolerance in patients with PD using flexible dosing, final mean doses were 7.8g and 4.8g^{14,15}.

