Sodium Oxybate in Treatment-Resistant REM Sleep Behavior Disorder (RBD): A Randomized Placebo-Controlled Trial

Statistical Analysis Plan

NCT04006925

January 11, 2023

Statistical analysis (using SAS 9.4, Cary, NC) was by intention-to-treat for the primary efficacy analysis, comparison of baseline characteristics, safety and tolerance and per-protocol (PP) for secondary/exploratory analyses. PP analysis included all participants who completed titration and the 4-week treatment period. Sample size calculation was based on a prior randomized controlled study by Brunetti et al.²⁵ To detect an effect size of 50% reduction in the number of RBD episodes per month ([placebo - active] / placebo) with a power of 80% and alpha of 5%, the number of participants needed to be 10 per arm. Anticipating a dropout rate of 20%, 24 participants required to be enrolled.

We tested the primary hypothesis that SXB is superior to placebo in reducing the number of RBD episodes from baseline, as observed in the last month of treatment using linear mixed effects models with random intercepts. Models were parameterized in two ways to estimate separate group trajectories and between-group differences in change over time. Cohen's d was calculated as a measure of treatment effect size. Similar hypotheses were tested on secondary and exploratory outcomes. Within- and between-group differences were assessed with paired- and unpaired t-tests, or with the Wilcoxon Signed Rank and Mann-Whitney U tests for nonnormal data. Bootstrapped percentile-based 95% confidence intervals were calculated based on 10,000 randomly resampled datasets. Participants scoring below 4 on the CGI-I and CGI-E were classified as "responders"; chi-square tests were performed to compare the proportion of responders between groups. All statistical tests were conducted using a 2-sided alpha level of 0.05. For secondary/exploratory analyses, bootstrapped percentile-based 95% confidence intervals were calculated based on 10,000 randomly resampled datasets. Descriptive statistics on safety data are provided for all randomized participants (intention-to-treat), by treatment group and study phase.

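### Time on blinded drug depends on response and tolerability and may differ by arm, but the SAP's safety summary by arm and study phase names no exposure time

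*SAP*

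**What the plan says.** The SAP deals with safety in its last sentence: "Descriptive statistics on safety data are provided for all randomized participants (intention-to-treat), by treatment group and study phase". Neither document mentions person-time, duration of exposure or exposure-adjusted rates. Tolerance and side effects are a secondary objective in the protocol.

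Phase length is set participant by participant. Under Trial Design, the dose is titrated weekly "to an optimal individual dose based on clinical response on RBD symptoms and tolerability". Treatment Regimen agrees ("until reaching the optimal dose based on clinical response and tolerance, not exceeding 9g nightly") and limits the intervention to "no longer than 12 weeks, including up to 8 weeks of flexible dosing and 4 weeks of stable dosing".

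The Flowchart supplies the days:
- Start of study drug: "Day 29 (One day after Day 28 ± 7 days, Visit #2 = Randomization visit with research coordinator").
- Interim visit: "Day 57-85 ± 7 days (Visit #3 = Interim visit with research coordinator").
- Final visit: "Day 85-113 (One day after Day 84-112 ± 7 days, Visit #4 = Final Visit with research coordinator").
- Weekly calls, at which adverse events are recorded: Days 30 to 84, ± 7 days.

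Other places in the protocol give a different treatment length. The Summary, the Hypothesis and the opening of Trial Design all describe an 8-week intervention.

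**The concern.** The flexible phase lasts as long as it takes to find a dose that works and is tolerated, so its length is partly a result of treatment. If the arms differ in response or tolerability, they can also differ in weeks at risk. A count or percentage of participants with an event, by arm and phase, then mixes the event rate with the length of observation. The mixing can create a difference between arms or hide one.

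The calls add a second problem. A participant who settles after 4 weeks has the stable phase at about Days 57 to 84, within the listed calls. One who titrates for 8 weeks enters the stable phase at about Day 85, when the listed calls have ended or, with the 7-day allowance, are about to end. How closely events are sought in the stable phase thus also depends on titration length.

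Safety is read descriptively here, from about 12 participants per arm, so readers will take the tabulated figures largely at face value.

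**Working it through.** **Phase lengths from the visit days** (taking Visit 3 as the end of flexible dosing, which is an inference):
- Flexible phase: (57 − 29)/7 = 4 weeks to (85 − 29)/7 = 8 weeks.
- Blinded treatment: (85 − 29)/7 = 8 weeks to (113 − 29)/7 = 12 weeks.
- Largest exposure ratio between participants: 8/4 = 2.0 in the flexible phase and 12/8 = 1.5 overall.

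**Direction.** From 4.5 g in steps of 1.5 g, the 9 g cap is reached after (9 − 4.5)/1.5 = 3 increases. In steps of 0.5 g it would take 9. A non-responder without side effects can therefore stop titrating early, while poor tolerability, with smaller steps or reversals, can prolong titration. Either arm could be the longer one.

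**Size with a constant hazard (assumed, equal in both arms).** P(at least one event) = 1 − exp(−h × weeks). The documents give no event rate, so a range is shown for the flexible phase:

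| h per week | 5 weeks | 7 weeks | Gap (points) | 4 weeks | 8 weeks | Gap (points) |
|---|---|---|---|---|---|---|
| 0.02 | 9.5% | 13.1% | 3.5 | 7.7% | 14.8% | 7.1 |
| 0.05 | 22.1% | 29.5% | 7.4 | 18.1% | 33.0% | 14.8 |
| 0.10 | 39.3% | 50.3% | 11.0 | 33.0% | 55.1% | 22.1 |
| 0.20 | 63.2% | 75.3% | 12.1 | 55.1% | 79.8% | 24.7 |

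At 0.10 per week, the gap is 12 × 0.110 = 1.3 participants for 5 versus 7 weeks and 12 × 0.221 = 2.7 for 4 versus 8.

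**Hidden excess.** A true rate ratio disappears when it equals the inverse ratio of exposures. At 5 weeks on sodium oxybate and 7 on placebo that ratio is 7/5 = 1.4: 0.14 × 5 = 0.10 × 7 = 0.70, so both arms show 50.3%. At 4 versus 8 weeks a doubling disappears.

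**Size with a front-loaded hazard (assumed: 0.30 per week for 2 weeks, then 0.02).** The cumulative hazard is 0.60 + 2 × 0.02 = 0.64 at 4 weeks and 0.60 + 6 × 0.02 = 0.72 at 8. The proportions are 47% and 51%, a gap of 4 points instead of 22. Here a simple rate per week would itself mislead: 0.64/4 = 0.16 against 0.72/8 = 0.09 for the same underlying hazard.

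**The two treatment lengths.** The stated supply is 5,292/12 = 441 g per participant. That equals 7 × (4.5 + 6 + 7.5) + 35 × 9 = 126 + 315 = 441 g over 21 + 35 = 56 nights, or 8 weeks. The same pattern over 12 weeks would need 126 + 63 × 9 = 693 g.

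**The case against.** Much can be said for the plan as it stands, and several points limit the concern.

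- Reporting by phase is a partial safeguard. The stable phase is planned at about 4 weeks for everyone who reaches it. This stands, but it leaves the flexible phase, the overall totals and the uneven call schedule.
- The SAP's silence does not exclude exposure-based reporting. That is true. But where phase length varies by participant, the plan should name the denominator.
- The 4-week lower end is not a protocol rule. The text gives only an upper limit of 8 weeks, and Visit 3 is labelled an interim visit. This stands. Some participants may settle sooner, so the first 4 weeks cannot be described as titration time for all.
- If treatment is fixed at 8 weeks, total exposure differs only through dropout. This also stands, although the split between flexible and stable weeks could still differ by arm.

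A reader might go further and infer that placebo non-responders titrate longest, so that a sodium oxybate excess is masked. The 9 g cap argues against assuming this. Nor do the documents support taking 4 versus 8 weeks for whole arms as the expected case.

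A reader might also infer that the primary efficacy comparison is biased, because the final treatment month falls at different times after randomisation. The documents do not establish this. Measuring response at the individually optimised dose fits the flexible-dose design, no time trend is quantified, and the clonazepam cross-taper is planned to finish within the first 2 weeks of study drug, before either possible window.

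**Conclusion.** The concern holds as a gap in the safety plan that should be closed. Time at risk can depend on treatment, the direction is unknown, and the planned summary names no exposure. With a constant 0.10 per week and 5 versus 7 weeks, the false difference is about 11 points. The 22-point gap at 4 versus 8 weeks is an upper extreme for that rate, and a front-loaded hazard reduces it to about 4. These sizes rest on assumed hazards and assumed average phase lengths, since the documents give neither by arm. A shift of 1 to 3 participants is within chance at 12 per arm, so the point is about making the tables interpretable. It does not show that the safety conclusion will be wrong. It calls for no change to the efficacy analysis.

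**What to change.** In the SAP:
1. Report weeks on blinded drug and length of the flexible phase, by arm.
2. Beside the counts by arm and phase, give adverse events per person-week on blinded drug.
3. Add adverse event tables for two windows measured from randomisation and common to both arms: the first 4 weeks, and the first 8 weeks, which is the shortest scheduled treatment time. Both lie within the listed weekly calls (Day 29 plus 8 weeks is Day 85). Do not describe the first 4 weeks as titration for everyone. These windows are needed as well as the rates, because person-week rates mislead when the hazard is front-loaded.

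In the protocol, the passages giving 8 weeks of intervention, those allowing up to 12, and the drug supply must be reconciled, and the days of the weekly calls set against the outcome.

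The cost is a few lines of SAP text and a few tables. The weekly calls and visits already collect adverse events; the tables also need each participant's dosing dates. The rates will be imprecise at 12 per arm, and early dropout still shortens follow-up within a common window, so the weeks of exposure should be shown there too.
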